Aim 3 (A3). Evaluate the impact of the staff intervention on resident falls, accidents and injuries and on quality of life using a prospective experimental design that derives information from five sources: (1) resident interviews (2) staff informants (3) observational data (4) chart and (5) incident/accident report data.

Primary Hypothesis: The frequency of falls, accidents and injuries will decrease in the

intervention group, relative to the comparison group after implementation of the training intervention.

Secondary Hypotheses: 1. Resident quality-of-life as measured by affective state will improve in the intervention group, relative to the comparison group after implementation of the training intervention.

2. Resident behavior problems will decline in the intervention group, relative to the comparison group after implementation of the training intervention. Resident behaviors will mediate the relationship between the intervention and the falls/accidents/injuries outcome.

Trial design

This is a pragmatic, prospective, cluster randomized trial (facility level) design with three waves of data collection (baseline, 6- and 12-months) at 12 assisted living facilities in two New York regions. There will be three levels of clustering: facilities within regions, units within facilities and repeated measures on residents within units, with the regions fixed. On a rolling basis, six facilities will be selected at random and recruited in New York City and the nearby suburban counties (downstate region). Six facilities in the upstate New York region of Rochester will also be randomly selected. Three facilities in each region will be randomized to usual care or to the intervention on a 1:1 ratio. Facilities allocated to the usual care group will receive the intervention after completion of their 12 month data collection.

Methods: Participants, interventions and outcomes

Study setting

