This measure was based on the Shift Coupon, a form originally designed by nursing staff to provide a “quick, easy, anonymous, and non-threatening method to report adverse events,”²¹ and is in the form of a small note pad. BRDSs are intended to measure recognition and capture real time R-REM events. Hypothesis 2, regarding enhanced R-REM recognition will be examined with a Chi-square analysis comparing counts of BRDS reports from experimental and comparison facilities captured over time, and treated as binary incidents. Reporting implementation will be examined by evaluating the differences between experimental and comparison group staff reports of R-REM, collected over three waves. Individual R-REM reporting will be determined by counting whether any of the staff-reported R-REM indicators are positive. The object of this analysis is not to identify individuals and perpetrators, but to examine the reported events. In modeling R-REM events, a Poisson regression of count data will be performed.

Aim 3: Primary level-4 evaluation of distal outcomes: Summary of the sources of data for determining falls/accidents/injuries and incidents of R-REM: The data used for evaluation of the primary distal outcome and for R-REM reports include (a) self-report among those residents who are capable, (b) Accident and Incident Reports, (c) resident record review, (d) observational data, including the BRDS, and (e) reports from staff. In addition, an environmental evaluation will occur. Data for falls and injuries will be collected via chart review, staff report and residents who can self-report, and from Incident/Accident Reports on an ongoing basis. Resident and staff informant information will be collected at baseline, 6- and 12-month follow-up. Falls will be considered as binomial (any fall) and Poisson distributed (fall counts).

Sample size {14}

Power calculations are provided for the primary distal outcome: falls, including accidents and injuries, also the outcome requiring the largest sample size. Upstate it is expected that an average

of 50 residents per site will be selected for a total of 300. Downstate, the facilities are larger, and it is expected that the average size will be 125 residents or 750 total. The proposed sample size is 6 facilities and 525 residents per arm.

Using the canonical link (Logit), the generalized linear model (GLIMMIX):

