$\eta = \log(p_{ijk} / (1 - p_{ijk})) = \beta_0 + \beta_1 X_{ijk} + FU_{jk}$, where FU_{jk} is a random effect associated with facility and unit.

The formula for the sample size per group using the method of Diggle is:

$m^* = (z_{\alpha} \sqrt{2PQ} + z_{\beta} \sqrt{p_0 q_0 + p_1 q_1})^2 (1 + (n-1)\rho) / (n(p_1 - p_0)^2)$; and using the GEE method:

$m^* = \frac{(Z_{1-\alpha/2} + Z_{1-\beta})^2 (\pi_1 p_0 (1 - p_0) + \pi_0 p_1 (1 - p_1)) (1 + (n-1)\rho)}{2n\pi_0\pi_1(p_0 - p_1)^2}$. The formula below is adjusted with variance inflation factor (V_{if}) and reliability(R_{el}): $m = V_{if}m^* / R_{el}$ and

$$V_{if} = (1 + (n_e - 1)\rho_e)(1 + (n_s - 1)\rho_s n_e p_e / (1 + (n_e - 1)\rho_e))$$

where $n_s = 5$ is the average number of units in the facility, $\rho_s = 0.015$ is the ICC for facility, $n_e = 17$ is the average number of residents in the unit, $\rho_e = 0.03$ is the ICC for unit, and the reliability:

$$R_{el} = 0.95.$$

The following table assumes $\alpha = 0.05$, power $(1 - \beta) = 80\%$, $R = 0.95$ and $V_{if} = 2.5$ (With $n_e = 17$,

$ICC_{Unit} = 0.03$, $N_s = 5$, $ICC_{Facility} = 0.015$, the fall rate at follow-up: $p_0 = 33\%$ and $p_1 = 20.75\%$). Two

scenarios for ρ (the average correlation of the outcomes over waves) were posited:

Group	Fall rate P(y=1)				Diggle Method		GEE Method	
	Baseline Rate	6 Month	12 Month	Combined 6M & 12M	M ($\rho = 0.5$)	M ($\rho = 0.6$)	M ($\rho = 0.5$)	M ($\rho = 0.6$)
Intervention	37%	22%	19.5%	20.75%	404	431	399	425
Usual Care	37%	34%	32%	33%	404	431	399	425

As shown, with 525 per group, power is adequate for intent-to-treat (ITT) analyses, including all respondents. Because randomization is at the facility rather than individual level, there is the potential for imbalance on baseline variables and missing covariate data. Assuming attrition of

15% at wave 1, it is estimated that 445 per group will have at least baseline and one additional wave of data included, using the EM missing data algorithm; thus, power is adequate to detect the posited difference in fall reduction of about 12% even with attrition.

Recruitment

All residents are approached and invited to participate. For those who do not wish to be interviewed, a different or the same interviewer approaches again at another time that may be more amenable to the resident. All resident questions are addressed and interviews occur at a time and place preferred by the resident.

Assignment of interventions: allocation

Sequence generation

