Algorithms for conducting randomization that take into account clustering such as exists with geographical regions and rolling enrollment have been developed by the author. This method has yielded balanced groups for many studies. This randomization procedure will be carried out using a SAS macro after a facility completes the baseline interview. A random number from 0 to 1 will be used to determine the assignment group. The standard cut score will be set at 0.5 for the first n facilities from the same region. Facilities which receive a random number between 0 and 0.5 will be assigned to the usual care group and those with a random number greater than 0.5 will be assigned to the intervention group. The balance between the groups within each group will be carefully weighted after the total number of facilities from a group reaches a number greater than n. Before the randomization procedure, the number of facilities randomized to each arm for each region will be estimated using SAS macro programs. If more than the n facilities are randomized initially, the cut score for the next facility is equal to the ratio of the intervention group (n1) to the facilities already randomized (m) for that group (n1/m). For example, group A region provides eight facilities for randomization and the n is set to 5, the first five facilities (n) will be randomized to the standard cut score 0.5 (about half will go to the intervention and half to the usual care group). The sixth facility's randomization cut score is equal to the number of facilities in the intervention

group (n_1) divided by the total number of facilities randomized within that group (in this case, the denominator m is 5.) The seventh facility's cut score will be adjusted according to the previous six facilities, and so forth.

Concealment mechanism

The biostatistician who runs the randomization procedure passes the information directly to the intervention trainer who alerts the ALRs of their assignment. The principal investigator who oversees the data coordinating centre (DCC) at the Research Division, Hebrew Home at Riverdale (RD-HHAR) is the only other person made aware of the assignment.

Implementation

A biostatistician at the coordinating centre developed and runs the randomization procedure. Randomization occurs at the facility level. Research interviewers who enrol participants are blinded to randomization group.

Assignment of interventions: Blinding

Who will be blinded

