Based on our experience in the conduct of many studies with residents in long term care facilities, we expect 15% attrition at 6 months and up to 40% at 12 months follow up, mainly related to discharge, hospitalizations and death. These percentages have been considered in the power calculations. All enrolled individuals who still reside at the facility at the follow-up visits will be invited to participate at follow-up at a convenient time for the respondent. Multiple attempts will be made to interview these residents.

Data management

Data entry and quality: All screening and evaluation data will be collected using a computer assisted personal interview (CAPI) system. This method provides accuracy in data collection, because the system does not accept out-of-range values, and does not allow for deviation from prescribed skip patterns. The DCC will create scoring and cleaning programs for scales within instruments. Although the CAPI and data entry systems should not allow these types of errors, the cleaning programs serve to double check the accuracy of the data. Periodically, the data manager will review all data for duplicate records, illogical collection dates or times of interview, outlier and out of range values, and illogical contingencies using program syntax created for each data file. After any corrections are made, items distributions will be reviewed to make sure no anomalies remain. In addition, the project coordinator periodically reviews entire files as a quality assurance measure.

Data storage, data safety and security: All laptops used for data collection and office based desktop computers are password protected and Bitlocker encrypted. Laptops will not leave the facility. Laptops with encrypted data are stored in a locked cabinet at the facility and not removed until study end. They are dedicated to the project and not connected to the internet. Log sheets will also be kept in a locked onsite storage area.

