Statistical methods appropriate for clustered data will be used in the primary analysis to compare the groups with respect to the binary outcome. Generalized mixed effects models (MEMs) will be used to test the hypothesis that those assigned to the intervention will experience a significantly higher rate of fall/accident/injury reduction as contrasted with usual care. The outcome will be modeled as a function of intervention, time and their interaction and controlling for the baseline falls. To account for the clustered nature of the outcomes, the models will include random effects for facilities, units and subjects. The models will be fit using mixed effects logistic-regression as implemented in SAS Proc Glimmix. The appropriate covariance structure will be determined. The primary analysis will be supplemented with an exploration of the effect of baseline subject, facility and unit characteristics on the intervention effect. These results will inform generalizability of

intervention effects.

Analyses for secondary outcomes: The proposed secondary outcomes are affect, measured by the FTQ and the NIH PROMIS depression measure,^{61,62,63} and behavior. The reliability estimates of the outcomes are typically at least 0.90. Methods for analyses of treatment effects in pre-post clinical trials, in the context of missing data, have been compared.^{64,65,66,67,68,69} The primary proposed analyses will use MEMs, and a full information likelihood approach, with sensitivity analyses using generalized estimating equations (GEE).

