Based on prior experience with the outcomes, it is not expected that transformations will be necessary. Baseline variables will be examined by study arm; however, no p values will be provided, and covariates (other than baseline values) are not proposed for inclusion in the main analyses of treatment effects.

Examination of potential region differences: Data from regions (upstate and downstate) will be combined and each outcome (e.g., depression, affect) modeled as a function of two factors (i) intervention, a factor with 2 levels and (ii) region, a factor with 2 levels, and the interaction between (i) and (ii). MEMs will be used for each outcome, e.g., depression, and likelihood ratio tests (χ^2) used to test for significance of the interaction term. The study is not powered to detect meaningful regional differences in treatment effect; therefore we will use $\alpha=0.15$ as a criterion, and explore if regional differences are related to differences in intervention effects.

Interim analyses

There are no plans for interim analysis or predetermined stopping guidelines.

Methods for additional analyses (e.g. subgroup analyses)

Heterogeneity of Treatment Effects (HTE): Because there is interest in examining subgroups to determine for which individuals interventions may be effective, we will perform descriptive HTE with potential effect modifiers as interaction terms. HTE will be examined for subgroups, e.g., those with and without cognitive impairment.

Methods in analysis to handle protocol non-adherence and any statistical methods to handle missing data

Examination of baseline differences on key variables between completers and those lost-to-follow-up will be conducted to inform about the nature of the missing data. The ITT analyses performed using MEMs will permit all individuals with at least one post-baseline observation to be included.

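### Power after attrition is not supported as written: normal quantiles for 12 facilities and only the 15% loss were used (about 70–80% once corrected, before baseline adjustment); the main model also lacks a df method and a region term

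*Combined protocol and SAP*

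**What the plan says.** **Sizing.** Under Sample size {14}, the plan takes two-sided 5% significance, 80% power, fall rates of 33% and 20.75% over the two follow-up waves, reliability 0.95 and variance inflation (Vif) 2.5. It tabulates 404 and 431 residents per arm (Diggle method) and 399 and 425 (GEE method) for between-wave correlations of 0.5 and 0.6. It plans 6 facilities and 525 residents per arm. It then applies 15% attrition to reach 445 per arm and concludes that "power is adequate to detect the posited difference in fall reduction of about 12% even with attrition".

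**Attrition.** The section on retention and complete follow-up expects 15% loss at 6 months and up to 40% at 12 months, and adds: "These percentages have been considered in the power calculations". The statistical methods section puts one-year loss at 30% to 40%.

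**Primary model.** "The outcome will be modeled as a function of intervention, time and their interaction and controlling for the baseline falls", with random effects for facilities, units and subjects, in Proc Glimmix. No denominator degrees-of-freedom method is named. Later text says that "covariates (other than baseline values) are not proposed for inclusion in the main analyses of treatment effects". Region appears only in a separate analysis of the region-by-intervention interaction.

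**Allocation.** Trial design calls the regions fixed and states: "Three facilities in each region will be randomized to usual care or to the intervention on a 1:1 ratio". Under Sequence generation, "The standard cut score will be set at 0.5 for the first n facilities from the same region"; after that the cut becomes the number already allocated to intervention divided by the number already randomized. The value of n for this trial is not given. Downstate, "the facilities are larger, and it is expected that the average size will be 125 residents or 750 total"; upstate the average is 50 residents.

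**The concern.** Vif inflates the variance for clustering. It does not allow for that variance having to be estimated from 12 facilities. With six facilities per arm, the reference distribution for the intervention effect is close to t on 10 df, or 9 with region, and the normal quantiles overstate power. The 445 retained residents are also compared with M values that assume two follow-up waves each, although many are expected to contribute only one.

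The same small number of facilities makes the df method matter for the primary p value, so it should be fixed before analysis. Region is a separate matter. If the regional mix differs between arms, a regional difference in falls enters the effect estimate unless region or baseline falls absorb it. If the split is exactly balanced, leaving region out mainly costs precision.

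**Working it through.** **1. The plan's own figures.** Let d = 0.33 − 0.2075 = 0.1225, so d² = 0.015006. Let S = 0.33×0.67 + 0.2075×0.7925 = 0.38554. With pooled P = 0.26875, 2PQ = 0.39305. Two waves; z = 1.960 and 0.842.

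- Vif = 1 + 16×0.03 + 4×17×0.015 = 2.50. The printed formula also carries a factor p_e; 2.5 is the value without it.
- Diggle, ρ = 0.5: (1.960√0.39305 + 0.842√0.38554)² × 1.5 / (2×0.015006) = 153.30; × 2.5/0.95 = 403.4. For ρ = 0.6: 163.52, giving 430.3.
- GEE, equal arms: 7.849 × 0.19277 × 1.5 / 0.015006 = 151.24, giving 398.0. For ρ = 0.6: 424.5.

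Rounded up, these are the stated 404, 431, 399 and 425. The table therefore contains normal quantiles and two complete waves.

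**2. Power at 445 per arm.** SE² = S × (1+ρ)/2 × Vif / (0.95 × 445). With Vif 2.5, d/SE = 2.96 (ρ = 0.5) and 2.87 (ρ = 0.6). Power from the normal, and from the noncentral t with critical values 2.228 (10 df) and 2.262 (9 df):

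| Vif | z | t, 10 df | t, 9 df |
|---|---|---|---|
| 2.5 | 84.2 / 81.8% | 76.1 / 73.4% | 75.1 / 72.4% |
| 2.27 (units shrink by 15% to 14.45) | 87.5 / 85.3% | 80.0 / 77.4% | 79.0 / 76.4% |

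Each pair is ρ = 0.5 / 0.6.

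**3. Adding 40% loss at 12 months.** Of 525, 315 have both waves (assuming everyone seen at 12 months was also seen at 6) and 445 − 315 = 130 have one. The two-wave equivalent is 315 + 130 × (1+ρ)/2 = 412.5 (ρ = 0.5) or 419 (ρ = 0.6).

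| Vif | z | t, 10 df | t, 9 df |
|---|---|---|---|
| 2.5 | 81.4 / 79.5% | 73.0 / 70.9% | 71.9 / 69.8% |
| 2.27 | 84.9 / 83.2% | 77.0 / 74.9% | 75.9 / 73.9% |
| 2.08 (clusters at 72.5% mean retention) | 87.8 / 86.2% | 80.4 / 78.5% | 79.4 / 77.5% |

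With 30% loss at 12 months, t gives 71–74% at Vif 2.5 and 75–78% at 2.27.

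**4. Unequal facilities.** Assume 17-resident units in both regions and 85% retained. Vif is then 1.82 for 50-resident facilities and 2.78 for 125-resident ones: 2.51 weighted by residents, 2.42 by inverse variance. Power with t is 72–77% at 445 per arm and 70–74% with 40% loss. A simulation of facility means with these sizes and 85% / 60% retention gave 72–75%.

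**5. What baseline adjustment must deliver.** 80% power with t on 9 df needs d/SE = 3.15. With 40% loss, the variance must fall by 1 − (2.852/3.15)² = 18% (ρ = 0.5) or 22% (ρ = 0.6) at Vif 2.5, and by 10% or 14% at Vif 2.27.

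**6. Reference distribution.** P(|t| > 1.96) on 10 df is 7.8%. This would be the type I error if a normal cut-off were used.

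**7. Allocation rule.** Applying the cut scores as written to six facilities in a region, with n assumed because it is not given:

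| n | 3:3 in one region | 3:3 in both | Regional mix differs between arms |
|---|---|---|---|
| 1 or 2 | 55.0% | 30.3% | 60.3% |
| 3 | 52.5% | 27.6% | 62.3% |
| 4 | 45.0% | 20.2% | 67.1% |
| 5 | 37.5% | 14.1% | 72.7% |

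For illustration, take 4:2 downstate and 2:4 upstate. The arms then hold 600 and 450 residents, with downstate shares of 500/600 = 83% and 250/450 = 56%. An assumed regional gap of 5–10 points in fall rate would shift the unadjusted effect by 1.4–2.8 points, against the posited 12.25.

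**The case against.** The strongest reply is that the primary model adjusts for baseline falls, so unadjusted power describes an analysis that will not be run. If the plan's ρ of 0.5–0.6 also held between baseline and follow-up, power after both corrections would be about 78–87% when only resident-level variance falls, and 87–95% if cluster variance falls too. This stands as a limit on the conclusion: the trial may well be adequately powered. But the sample size section claims no such gain and gives no baseline correlation.

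Attrition is also not the main driver. With z quantiles, the 12-month loss alone leaves 79–85% (up to 88% at Vif 2.08). That is correct. The shortfall comes chiefly from the t quantiles: even with no attrition, 80% power needs 491–524 per arm (10 df) or 504–537 (9 df), against 525 planned.

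Holding Vif at 2.5 while residents leave is pessimistic. Scaling it to the reduced sample gives 2.17–2.19 and power of 75–79%, or 71–76% with unequal facilities. All of this stays within 70–80%.

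Falls are also taken from charts and incident reports on a continuing basis, so a missed interview need not mean a missing outcome. This could soften step 3, but the plan does not say how partial follow-up is scored, and step 2 does not depend on the 12-month loss.

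Finally, the plan never prescribes a 1.96 cut-off for the test, the allocation text promises that balance will be weighed, and baseline falls should absorb much of a standing regional difference. These are fair. The 7.8%, the allocation probabilities and the 1.4–2.8 points therefore show what is left open; they do not predict what will happen.

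**Conclusion.** The concern holds. The table's arithmetic is right, but the statement of adequate power after attrition rests on quantiles and retention that do not match the design. At the plan's own 445 per arm, t quantiles alone bring power to 72–76% at Vif 2.5, or 76–80% at 2.27. With up to 40% loss at 12 months it is about 70–80%. The statement that both attrition figures were considered is not borne out by the sample size section, which applies only the 15%.

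These figures assume 9–10 df, the plan's rates, ICCs and reliability, and no gain from baseline adjustment. They show that adequacy is not demonstrated, not that the trial is certainly underpowered. Leaving region out of the main model conflicts with the design's description of regions as fixed. The unnamed df method and the unstated n are, taken alone, closer to missing detail, but both bear on the primary test.

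**What to change.** 1. Restate M and power with t quantiles on 9–10 df, 85% observed at 6 months and 60–70% at 12 months, and facilities of 50 and 125 residents. Give the result as a range over Vif, with and without baseline adjustment, and state the baseline correlation assumed.
2. Correct the retention section's sentence about what the power calculations considered.
3. Name a facility-level denominator df method for the intervention effect in Proc Glimmix (Kenward-Roger or between-within, about 9 df) and a small-sample-corrected variance for the GEE sensitivity analyses.
4. Add region as a fixed effect in the primary and secondary models, and amend the sentence that restricts covariates to baseline values.
5. State n, and reconcile the cut-score rule with three facilities per arm in each region.

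The cost is SAP wording and a re-run power table. The downsides are one df for region (about one point of power before any gain in precision), slightly wider intervals and a less favourable stated power.

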Analyses for the primary hypothesis for the distal outcome: The primary analyses will examine, on an ITT basis, the differences between the usual care and intervention groups in the reduction of falls/accidents/injuries over time. Other approaches, e.g., the analysis of the “as treated” sample can result in biased estimates of the causal treatment effect due to compromised random assignment. Our primary approach to analyses is guided by our own experience,⁵⁷ and reviews.^{58,59} Depending on the level of missing data, analytic strategies (see below) can be used to address non-compliance, e.g.⁶⁰ Based on prior trials that we have coordinated, sampled from this population, 1 year attrition is between 30% and 40%; thus for 6-month data (projected attrition of 15%), the ITT analyses of all subjects will be feasible. Longitudinal analyses will include those with at least baseline and one follow-up. Sensitivity analysis will be performed using multiple imputation under different assumptions for missing data.

Because randomization is at the facility rather than individual level, imbalance may be observed on baseline variables. Preliminary analyses will be performed to determine whether the groups are balanced. Two-tailed tests of significance will be performed. Binomial tests are to be conducted on dichotomous variables, Poisson tests on nonbinomial (e.g., count) data, and *t* tests on ordinal data, adjusting standard errors for clustered data within facilities; *p* values are reported because the design does not permit randomization at the level of the individual.

Effect on likelihood of falls/injuries/accident reduction:

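### The sample-size formula lets facility and unit variance average out over the two follow-up waves without saying so, and the claim of adequate power after attrition rests on that

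*Combined protocol and SAP*

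**What the plan says.** All references are to the combined protocol and SAP.

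- **Sample size {14}.** The logit model has a term FU with facility and unit subscripts, which "is a random effect associated with facility and unit". The per-arm number m* contains (1+(n−1)ρ)/n, where ρ is the correlation of a resident's outcomes over waves. It is then multiplied by V_if = 2.5 and divided by a reliability of 0.95. The rates, 33% and 20.75%, are those under "Combined 6M & 12M". For 80% power the table requires 404 (ρ = 0.5) or 431 (ρ = 0.6) per arm by the Diggle method, and 399 or 425 by GEE. With 525 enrolled and 15% lost, 445 remain, and "power is adequate to detect the posited difference in fall reduction of about 12% even with attrition".
- **Effect on likelihood of falls/injuries/accident reduction.** For the primary analysis, "the models will include random effects for facilities, units and subjects". No cluster-by-time effect is named. The model adjusts for baseline falls, and the covariance structure is left to be determined.
- **Plans to promote participant retention and complete follow-up.** Expected attrition is 15% at 6 months and up to 40% at 12 months: "These percentages have been considered in the power calculations".
- **Statistical methods for primary and secondary outcomes.** "Two-tailed tests of significance will be performed".

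**The concern.** A second follow-up wave averages out part of a resident's own variation. It does not average out a facility or unit effect that is the same at both waves. Multiplying V_if by (1+ρ)/2 shrinks the cluster component by the same 25% (ρ = 0.5) or 20% (ρ = 0.6) as the resident component. If the cluster effects persist, as the written models imply, the required number is too low and the margin between 431 and 445 disappears. With 12 randomised facilities the cluster component is the larger part of the variance, so this is not a minor term. A null result would then be read against more power than the stated assumptions support.

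**Working it through.** **Inputs.** From Sample size {14}: two-sided α 0.05, power 80%, p0 = 0.33, p1 = 0.2075 (difference 0.1225), reliability 0.95, 17 residents per unit, 5 units per facility, unit ICC 0.03, facility ICC 0.015, ρ 0.5 or 0.6, 6 facilities and 525 residents per arm, 445 after attrition, facility averages 50 and 125. From the retention section: attrition 15% and 40%. The number of waves n is 2; n = 3 does not reproduce the table.

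**1. The plan's own table.** V_if = 1 + 16(0.03) + 4(17)(0.015) = 2.50. Before inflation:
- GEE: (1.960 + 0.842)² × (0.33×0.67 + 0.2075×0.7925) / 0.1225² = 201.7.
- Diggle (pooled variance under the null): 204.4.

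Multiplying by (1+ρ)/2 × 2.5/0.95 gives 403.4 and 430.3 (Diggle) and 398.0 and 424.5 (GEE). Rounded up, these are the printed figures, so the two factors are indeed multiplied.

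**2. What the product assumes.** If facility and unit effects correlate across waves at c, the variance factor is (1+ρ)/2 + (V_if − 1)(1+c)/2.
- c = ρ gives the plan's product: 0.75 × 2.5 = 1.875 and 0.80 × 2.5 = 2.00.
- c = 1 (no time component) gives 0.75 + 1.5 = 2.25 and 0.80 + 1.5 = 2.30, larger by 20% and 15%.

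Required per arm at c = 1, as 204.4 or 201.7 times the factor over 0.95: 484 and 495 (Diggle), 478 and 488 (GEE).

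**3. Power at 445, equal facilities, no baseline adjustment.** The effective n is 445 × 0.95 / factor. For GEE, power = Φ(0.1225/√(0.38554/n_eff) − 1.960); the Diggle version uses the pooled variance 0.39305 in the critical value. The last column uses noncentral t on 10 df (12 facilities, two arms). Pairs are ρ = 0.5 / 0.6.

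| Form | V_if | Factor | Diggle | GEE | t, 10 df |
|---|---|---|---|---|---|
| Product (plan) | 2.5 | 1.875 / 2.00 | 83.7 / 81.3% | 84.2 / 81.8% | 76.1 / 73.4% |
| Additive | 2.5 | 2.25 / 2.30 | 76.6 / 75.7% | 77.2 / 76.3% | 68.4 / 67.5% |
| Additive | 2.305 | 2.055 / 2.105 | 80.3 / 79.3% | 80.8 / 79.8% | 72.3 / 71.3% |

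The third row is needed because 17 per unit means 5 × 17 × 6 = 510 residents per arm, not 445. With 30 units, 445 means 14.8 per unit, and V_if = 1 + 13.8(0.03) + 4(14.8)(0.015) = 2.305.

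**4. Facilities of 50 and 125, attrition 15% and 40%.** Assume three facilities of each size per arm, units of 17 at enrolment and monotone loss. Then 315 residents (60% of 525) have both waves and 131.25 (25%) only the first. Weight each resident by the inverse of own variance. For ρ = 0.5 and c = 1:
- resident part: 1/(315/0.75 + 131.25) = 0.001814
- sums of squared weight shares: residents 0.00228, units 17/525 = 0.03238, facilities 3(50² + 125²)/525² = 0.19728
- unit part: 0.03(0.03238 − 0.00228) = 0.000903
- facility part: 0.015(0.19728 − 0.03238) = 0.002474
- n_eff = 0.95/0.005191 = 183.0; power 75.5% (Diggle) or 76.1% (GEE)

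For ρ = 0.6, n_eff is 179.9 and power 74.8% or 75.4%. Weighting facilities by inverse variance instead gives n_eff of 191.1 and 187.5, and power of 76.5-77.9%. Overall this is about 75-78%, or 66-69% on 10 df. With c = 0.75 the same calculation gives about 78-81%.

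**5. Attrition.** 525 × 0.85 = 446, the source of 445. No 40% term appears in the formulae, the table or that count.

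**The case against.** Four points deserve weight.

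- **The sizing equation is schematic.** It has no time index on any term and no resident effect, so a missing index on FU is weak evidence of a commitment, and the covariance structure is left open. This stands in part: the product form is an undeclared assumption, not a slip in arithmetic. But nothing in the plan states or supports a cross-wave cluster correlation of 0.5 to 0.6.
- **The plan promises no specific power at 445.** A reader might infer that 80% is stated with attrition and that 75-77% is what the trial has. The documents support neither. The 80% belongs to the 399-431 in the table; at 445 the text says only that power is adequate. The 76-77% pairs 445 residents with a unit size that belongs to 510. With consistent unit sizes and equal facilities, the multiplication alone brings power to about 79-81%, which removes the margin rather than clearly missing the target.
- **Baseline adjustment.** The primary model adjusts for baseline falls. If cluster effects are constant over time, baseline carries them too, and adjustment removes some of that variance. As an illustration, take a linear-scale factor of (1+ρ)/2 + 1.5 − 2b(r + 1.5) + 2.5b². An assumed baseline-to-follow-up correlation and slope of b = r = 0.2 gives 1.67 or 1.72, and power at 445 of roughly 87-88%. The 0.2 is not in the documents and equal facilities are assumed, so this shows only that the gain could be material. The plan's calculation takes no credit for it.
- **Attrition.** The 445 counts residents with baseline and at least one follow-up, so 12-month loss does not change the count. That is right, but the formula then treats all 445 as contributing two waves.

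**Conclusion.** The point holds as an undeclared assumption that flatters the stated precision, together with an internal inconsistency on attrition. If facility and unit effects persist over the two waves, the variance factor is 15-20% larger than the plan's and the required number is 478-495 per arm at V_if 2.5. Power at the expected 445 is then about 75-81% (normal approximation, unadjusted) rather than the 81-84% implied by the plan's formula. The upper end assumes equal facilities, unit sizes that shrink with attrition, and 15% loss only. The lower end adds the plan's facility sizes and 40% loss at 12 months. A cross-wave cluster correlation of 0.75 in that harder setting gives 78-81%. Using 10 df lowers every figure, including the plan's own, so that loss is not due to the multiplication.

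It would go too far to conclude that the trial is underpowered. Before attrition, 525 per arm still gives 82-84% under the additive form at V_if 2.5, and the gain from baseline adjustment cannot be fixed from the documents.

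**What to change.** - Recompute the table with the additive factor, or state and justify the cross-wave correlation of facility and unit effects that the product form needs.
- Use facility sizes of 50 and 125, unit sizes that fall with attrition, and attrition of 15% and 40%.
- Replace the sentence on adequate power with a range and its assumptions (about 75-81%, normal approximation, unadjusted). Give the same range on 10 df.
- State any credit taken for baseline adjustment and the correlation behind it.
- Reconcile the retention section's statement on attrition with the sample-size section, which applies only 15%.

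This needs no new data and no change in enrolment. The cost is some recalculation and a slightly less favourable stated figure.
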